List placebo if it is considered a drug (contains more than inactive ingredients). For example, normal saline is considered a drug that should be listed, whereas placebo tablets are usually inert ingredients that do not need to be listed.

b) Please list in the space below all investigational drugs, reagents or chemicals to be administered to subjects during this study. Attach all applicable Investigator Brochures in section #16 (Attachments).

c) Please list in the space below all FDA approved drugs, reagents, chemicals to be administered to subjects during this study. Attach all applicable package inserts in section #16 (Attachments).

d) Please list in the space below all dietary supplements, vitamins, minerals, or foods to be administered to subjects during this study.

Please read the IND Statements.

* * * Other Levels Of Review * * *

7. Other Levels Of Review

1. University Radiation Safety

Protocols that involve non-standard of care radioactive materials (which includes the terms "radioisotopes", "radionuclides", "radiopharmaceuticals", and "nuclear medicine studies", e.g., "PET", "MUGA", "Zevalin", and/or specific radionuclides such as "F-18", "Tc-99m", "Th-201", "I-131", "Ra-223", "Y-90", etc.) will receive review by the Radiation Safety Officer (RSO) and/or Radiation Safety Committee (RSC). For information on how to submit for radiation safety review, see RSC instructions or contact the Radiation Safety Officer at [name].

Not Applicable

Yes, study involves radioactive materials (per instructions, submit to RSC before IRB)

2. Institutional Biosafety

Experiments involving the deliberate transfer of Recombinant or Synthetic Nucleic Acid Molecules (e.g., Gene Transfer), or DNA or RNA derived from Recombinant or Synthetic Nucleic Acid Molecules, or Microorganisms containing Recombinant or Synthetic Nucleic Acid Molecules and/or infectious agents (including select agents and toxins as defined by CDC and/or Animal and Plant Health Inspection Service (APHIS)) into one or more human research participants must be reviewed by the SLU Biological Safety Officer. Most of these protocols also require review and approval by the SLU Institutional Biosafety Committee (IBC). Please contact the SLU Biological Safety Officer at [name] for more information.

Not Applicable

Yes, study requires Institutional Biosafety review

3. Pharmacy, Therapeutics, Nutrition, and Transfusion (PTNT) Committee

Saint Louis University Hospital requires that all research involving the administration of medications within the hospital (including outpatient areas such as the Emergency Department, Outpatient Center, Saint Louis University Hospital-South Campus, etc.) be reviewed and approved by the Pharmacy, Therapeutics, Nutrition, and Transfusion (PTNT) Committee and that study drugs are received, stored, prepared, and dispensed by the Hospital's Department of Pharmacy Services. Please contact the Investigational Drug Services Clinical Pharmacist at [name] or [contact] for more information.

Not Applicable

Yes, study requires PTNT review

4. Saint Louis University Hospital

All research involving Saint Louis University Hospital, including the Emergency Department, inpatient or outpatient services (including outpatient surgery at ABI and the infusion center at DOB) and medical record access, requires approval from the Saint Louis University Hospital Research Review Committee prior to study initiation. This process is designed to facilitate compliance with state and federal regulations as they pertain to research in hospitals and clinical research billing. Documents should be submitted as soon as possible, or at the latest, concurrently with IRB submission. Please contact the Research Compliance Office at [name] or [contact] of the SLU Clinical Trials Office (CTO) at [name] or [contact] for more information.

Protocol Title: Sensitivity and specificity of digital ankle brachial index (ABI) as a screening tool in detecting peripheral arterial disease: A single center, prospective clinical trial

Not Applicable

Yes, study requires Saint Louis University Hospital review

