f) Does the study include an investigator's brochure (IB)?

If yes, what is the current version date?

(If study has multiple IBs, attach current versions in Attachments section (#16))

Protocol Title: Sensitivity and specificity of digital ankle brachial index (ABI) as a screening tool in detecting peripheral arterial disease: A single center, prospective clinical trial

16. Provide a summary of any recent findings, literature, or other relevant information (especially pertaining to risks), if applicable.

Of the 238 subjects with usable data, QuantaFlo detected positive results for Peripheral Artery Disease in 44 subjects: 10 with severe, 15 with moderate, and 19 with mild disease. Of the 10 designated severe by QuantaFlo, 8 were confirmed upon follow-up exams and imaging (positive predictive value of 67%). Of those 34 designated mild or moderate by QuantaFlo, 2 were confirmed upon follow-up exams and imaging (positive predictive value of 14%).

17. Have there been any significant amendments or revisions to the protocol during the past approval period? (Significant amendments include changes in study design or risk level including those that resulted in a change in consent).

N

If yes, please briefly summarize the changes:

18. Y The consent materials attached to this eIRB application (including consent documents, assent documents, recruitment statements or other materials used to obtain consent) are the versions being used in the conduct of this study and all enrolled subjects have signed consent forms on file, if required. (If the requirement to obtain consent was waived or if no participants have enrolled since last continuing review, check N/A).

NOTE: The IRB routinely monitors consent document usage and may request copies of redacted participant consent forms.

19. Are any changes (amendments) requested with this Continuing Review?

Y Yes, please complete the remainder of this form.

No, form is complete. Please submit.

20. Summarize the proposed changes to the protocol in lay terms, including the type of change AND what the change involves.

If this is a change in PI a new Department Chair review is required. Please upload the signed document in the Attachments section.

We would like to increase the sample size from 400 to 750. This change involves using the same protocol on additional subjects by re-instituting the workflow at screening locations. We are also adding a study team member, [name].

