21. Provide justification/explanation for the proposed changes.

Given the low PPV of QuantaFlo, and considering the manufacturing company has different results, we would like to continue the study and increase enrollment to increase the power of our analysis.

22. Will currently accrued subjects need to be notified of changes?

N

If no, please justify why not.

All subjects who have been accrued have completed all study activities and will not be affected by additional subjects being accrued.

additional subjects being accrued.

If yes, please explain how AND when notification or re-consenting will occur.

23. Does the SLU IRB Protocol need to be modified? Y

24. Are consent documents modified? Y

Proceed to the appropriate section(s) of the protocol and make your changes. Also make necessary changes in the Consent Form(s), Assent Form(s), Recruitment Statement, Questionnaire, or other attachments, as applicable. Upload any revised IRB materials. Please provide the entire revised document (not just revised pages). Use track changes or highlight (in yellow) changes to documents being revised. Please upload a tracked/highlighted copy of each revised document to be stamped upon IRB approval. NOTE: Upload a clean copy (changes or highlights removed) of documents in file formats other than Microsoft Word (i.e., the IRB will remove the tracked changes/highlights on uploaded Word documents).

NOTE: Protocol amendments must receive IRB review and approval before they are implemented, unless an immediate change is necessary to eliminate an apparent hazard to the subjects.

Sponsored Studies: Remember to update the Sponsor's Protocol version number and date in the Funding section of the protocol (this information will appear on the approval letter).

List of changed sections:
Personnel Information
Subject Population 8(a-g)
Informed Consent (13)

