ABI ≤ 0.9 has been used as the criterion for diagnosing PAD based on ACC/AHA guidelines for the management of patients with PAD [3]; the cutoff value of ABPI ≤ 0.9 it has been reported that the sensitivity of diagnosing PAD was 83% to 85% and a specificity of 95% to 100% [5]. ABI has been validated against lower extremity contrast angiography obtaining high sensitivity (85%–95%) and specificity (90%–100%), for diagnosing PAD [6, 7]. Many studies have reported more than 95% of sensitivity and specificity of colour duplex ultrasound scan in detecting a significant stenosis of the arteries [8, 9].

Please save frequently

b) Describe any animal experimentation and findings leading to the formulation of the study, if there is no supporting human data.

Protocol Title: Sensitivity and specificity of digital ankle brachial index (ABI) as a screening tool in detecting peripheral arterial disease: A single center, prospective clinical trial

N/A

2. Purpose of the study

a) Provide a brief lay summary of the project in <200 words. The lay summary should be readily understandable to the general public.

QuantaFlo™ (Semler Scientific, Inc.) is a novel, noninvasive, 510K FDA approved digital device that is used as a screening tool to measure ABI of patients at risk of PAD. This single center prospective clinical trial will evaluate the sensitivity and specificity of digital ABI in detecting PAD using color Doppler ultrasound and 'gold standard' angiography as reference. Specifically in participant undergoing dialysis and who cannot undergo ABI using pressure cuffs dialysis grafts/ fistulae in the arms, we will evaluate the value of digital ABI in detecting PAD.

Page numbers from a sponsor's protocol/grant may be referenced in 2b and 2c.

b) List your research objectives (specific aims & hypotheses of the study).

Primary aim:

To evaluate the sensitivity and specificity of digital ABI in diagnosing PAD using color Doppler ultrasound and 'gold standard' angiography as reference.

Secondary aim:

- To correlate the digital ABI index with symptoms of PAD.
- To evaluate the value of digital ABI in detecting PAD in patients on dialysis in whom the presence of dialysis grafts/ fistulae in the arms would have prohibited the use of ABI using pressure cuffs.

Please save frequently

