c) Describe the study design (e.g., single/double blind, parallel, crossover, control, experimental, observational, etc.). If the study is investigator-initiated, a timeline for individual subject recruitment, follow-up, and analysis for the study is required. Also, indicate if the subjects will be randomized.

This is a pilot, Single Center, Prospective study. A total of 100 participants will be enrolled

d) If subjects will be given placebo, please justify placebo use. *?HELP?*

N/A

3. Study Procedures

a) N Is this project a multicenter study (i.e., same project is conducted elsewhere by a different investigator) OR does this study involve conduct of research at multiple sites?

Is SLU acting as a coordinating center for other sites OR is the SLU PI a direct recipient of a federal grant for this research? If yes, complete and attach the Supplemental Application for Coordinating Center Activities.

Protocol Title: Sensitivity and specificity of digital ankle brachial index (ABI) as a screening tool in detecting peripheral arterial disease: A single center, prospective clinical trial

Will the SLU site be participating in all parts/procedures/arms of the study?
If No, explain what SLU will NOT participate in:

Please save frequently

Page numbers from a sponsor's protocol/grant may be referenced in 3b, 3c, and 3d.

b) Describe all the procedures, from screening through end-of-study, that the human subject must undergo in the research project, including study visits, drug treatments, randomization and the procedures that are part of standard of care. Specify which procedures are for research and which are standard of care. Please note: The box below is for text only. If you would like to add tables, charts, etc., attach those files in the Attachment section (#16).

1. Screening sites: The digital ABI screening test will be offered at various outpatient clinics in departments belonging to family medicine, endocrinology, geriatric medicine.
2. Participant information: Participant will get information about Peripheral arterial disease based on a poster which will be placed in the waiting areas as well as flyers that will be presented to them during their routine clinic visit to the respective specialists.

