*** Subject Population ***

8. Subject Population - In the space below, please detail the participants that you are requesting to recruit (include description of each group requested)

a) Expected age range of subjects. (For example ≥ 18 yrs to 90 yrs).

18 years to 90 years old

b) Number of evaluable subjects to be accrued at SLU or SLU site (this includes all sites under the direction of the SLU PI).

Exceeding the number listed here is a protocol violation. Prior IRB approval is required if additional participants are to be accrued. If applicable, this number should be consistent with your power analysis described in 3d.

Protocol Title: Sensitivity and specificity of digital ankle brachial index (ABI) as a screening tool in detecting peripheral arterial disease: A single center, prospective clinical trial

c) Number of evaluable subjects to be accrued study wide. *?HELP?* 750

d) If including vulnerable populations (minors, pregnant women and fetuses, neonates, non-English speaking, economically or educationally disadvantaged, prisoners, adults temporarily or permanently unable to consent for themselves): 1) provide the rationale for the importance of including this population in the research, and 2) specify the measures being taken to minimize risks to potentially vulnerable subjects. Click on hyperlinks to access SLU Guidelines containing additional considerations and strategies for mitigating risks. n/a

e) If women, minorities, or minors are not included, a clear compelling rationale must be provided unless not applicable. Examples for not including minors: disease does not occur in children; drug or device would interfere with normal growth and development; etc. If federally funded reference appropriate section of the sponsors protocol/grant. *?HELP?* Minors will not be included in this study as they do not present to the study locations nor are they at risk of PAD.

f) If any specifically targeted subjects are students, employees, or laboratory personnel, specify the measures being taken to minimize the risks and the chance of harm to these potentially vulnerable subjects. See SLU Guidelines for additional considerations and strategies for mitigating risks.

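### Section 2c still describes a pilot of 100 while 8c says 750 evaluable; the PPVs behind the extension do not match their counts, and a larger N can narrow the PPV but cannot resolve sensitivity.

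*Combined protocol and SAP*

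**What the plan says.** Section 2c (study design) reads "This is a pilot, Single Center, Prospective study. A total of 100 participants will be enrolled". Section 8c reads "Number of evaluable subjects to be accrued study wide. *?HELP?* 750". Both are fields of the current application. Continuing review item 20 says "We would like to increase the sample size from 400 to 750", and the list of changed sections that follows names personnel, section 8 items a to g, and section 13. It does not name 2c.

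Item 21 gives the reason for the increase: "Given the low PPV of QuantaFlo, and considering the manufacturing company has different results, we would like to continue the study", and to "increase enrollment to increase the power of our analysis". It states no target precision, effect size or calculation. The results behind that reason are in item 16: "Of the 238 subjects with usable data, QuantaFlo detected positive results for Peripheral Artery Disease in 44 subjects", made up of 10 severe, 15 moderate and 19 mild. Item 16 reports 8 of the 10 severe as confirmed, with a PPV of 67%, and 2 of the 34 mild or moderate as confirmed, with a PPV of 14%.

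The primary aim in 2b is "To evaluate the sensitivity and specificity of digital ABI in diagnosing PAD using color Doppler ultrasound and 'gold standard' angiography as reference". Under 3b (clinical course), a participant diagnosed with PAD is advised about further testing or referral; where there is no evidence of PAD, nothing further is done. Section 3d describes a comparison with angiography only for a positive ABI. Section 8k says that further testing is standard of care and that its results are read from the records.

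**The concern.** A reader meets two planned sizes, 100 and 750, and no calculation for either. The reason for the larger one is power, yet the primary aim needs reference results in ABI negatives as well as positives, and the plan gives negatives no route to one. A reader could therefore take 750 as the sample behind the sensitivity estimate, when a large majority of those participants would contribute no planned reference result.

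The extension also rests on interim PPVs that disagree with the counts printed beside them. Until that is settled, it is unclear how many positives were verified, and so what the PPV is or how precisely it is known.

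**Working it through.** **1. Planned size.** 2c says 100; 8c says 750; item 16 already reports 238 usable. No alpha, power, prevalence or precision target is given, so neither planned size can be reproduced.

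**2. Printed PPVs (item 16).**
- Severe: 8/10 = 80.0%; printed 67%. With 8 confirmed, the only whole-number denominator that rounds to 67% is 12 (8/12 = 66.7%). Twelve exceeds the 10 severe results reported.
- Mild or moderate: 2/34 = 5.9%; printed 14%. With 2 confirmed, the only denominator that rounds to 14% is 14 (2/14 = 14.3%).
- The two discrepancies run in opposite directions. Pooled, the PPV is 10/44 = 22.7% on the printed counts and 10/26 = 38.5% on the denominators implied by the percentages.

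**3. Expected positives at 750.**
- Rate: 44/238 = 18.49%, exact (Clopper-Pearson) 95% CI 13.77% to 24.01%.
- Expected: 750 × 0.1849 = 138.7, or 139. The other 750 − 139 = 611 are expected to be negative.
- Range if the 238 count toward 750: 44 + 512 × (0.1377 to 0.2401) = 114 to 167.
- Range if all 750 are new: 750 × (0.1377 to 0.2401) = 103 to 180.
- These ranges carry only the uncertainty in the rate. Adding binomial sampling gives 110 to 171 and 99 to 184.
- The step from 400 to 750: 350 × 0.1849 = 64.7 more positives and 285.3 more negatives.

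**4. Sensitivity.** Assume that all 44 positives were verified, that the 34 not confirmed had no PAD, and that a share f of ABI negatives has PAD. The documents do not give f. With 10 confirmed and 238 − 44 = 194 negatives, sensitivity = 10/(10 + 194f):

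| f | Sensitivity | Specificity |
|---|---|---|
| 0% | 100% | 85.1% |
| 1% | 83.8% | 85.0% |
| 5% | 50.8% | 84.4% |
| 10% | 34.0% | 83.7% |

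At 750, both terms grow by 750/238, giving 31.5/(31.5 + 611.3f). N cancels, so the spread across f stays the same at 238, 400 or 750.

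**5. Specificity.** On the same assumptions it is 194(1 − f)/[194(1 − f) + 34], shown in the last column. The spread is 85.1 − 83.7 = 1.4 points. For any fixed f its 95% (Wilson) half-width does fall with N, from about 4.6 to 5.0 points at 238 to about 2.6 to 2.8 at 750.

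**6. PPV.** Interval width scales roughly with one over the square root of the number verified. If the PPV and the verified share stay as they are, the width at 750 is about √(238/750) = 0.56 of the present width. No absolute half-width is given here, because step 2 leaves the number verified unclear.

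**The case against.** The strongest reply is that section 8 governs accrual, so the line in 2c is a leftover that changes nothing in conduct. That stands. A reader might even infer from 2c that 238 usable subjects breached an enrolment cap of 100. The documents do not support this: the form ties the limit to the section 8 number, and item 20 gives 400 as the size before the change.

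A second reply is that the form asks for a power analysis only from full board, unfunded studies, whereas this study has a microgrant and marks expedited categories. That also stands. No breach is alleged, and 3d contains no power statement to correct. The word comes from item 21, and the point is only that the reason given there does not serve the primary aim.

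A third reply is that some ABI negatives may have reference imaging. The clinical course in 3b depends on the questionnaire as well as the digital ABI, and 3f says that patients with signs and symptoms have traditional ABI or Doppler ultrasound as standard practice. So 611 is not a fixed count of participants without any reference result. The plan still gives no route for using such results, and those imaged would be a selected group.

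Finally, a reader might infer that a larger N leaves specificity as unresolved as sensitivity. The figures do not support that. Reference results are missing in negatives for both, but specificity varies by only 1.4 points over the range examined and its sampling interval narrows.

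**Conclusion.** The conflict between 2c and 8c is real and sits in current text; alone it is minor. The item 16 PPVs are inconsistent with their counts (80% against 67%, and 5.9% against 14%). Since item 21 relies on them, they need correcting. This does not show that the reason for extending was false: the mild or moderate PPV is low on either reading.

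The extension to 750 buys about 139 positives, fewer with a reference result because testing is only advised and read from records. That can narrow the PPV. It does not resolve sensitivity, which runs from 84% to 34% as the assumed PAD rate in negatives goes from 1% to 10%, at any N. Those values also assume that all 44 positives were verified and that the 34 unconfirmed were free of PAD, which item 16 does not establish.

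**What to change.** 1. In 2c, state 750 evaluable to agree with 8c, and remove the word pilot or reconcile it with that size.
2. In item 16, correct the PPVs or their denominators against source data and state how many positives were verified. Quote no PPV precision until that is done.
3. Correct the reason in item 21, or add a sentence to 3d, along these lines: *At the positive rate seen so far (44 of 238, 18.5%), 750 evaluable participants are expected to give about 139 positive digital ABI results (about 114 to 167 if the 238 count toward 750; 103 to 180 if not), of whom fewer may have a reference result. This number supports the precision of the positive predictive value; it does not provide power for sensitivity.* Say which of the two counting rules applies.
4. Keep the primary aim in 2b and state this limit beside it. Changing the aim to PPV after seeing the interim PPV would be data-driven.

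Showing the PPV before and after the extension is optional. The cost is wording in a few places and one check of source data, with no added participants or procedures. The stated information will look smaller than 750 suggests.

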
7. Clinical course: If based on Screening questionnaire and digital ABI,
I. Participant is diagnosed with PAD- the referring physician and participant will receive a phone call about the same. He/ she will then be advised any further testing/ referral to IR clinic.
II. There is no evidence of PAD- no further action will be taken. The participant will be informed of the same.

8. The data of all patients who have answered the questionnaire will be accessed. This includes those patients who are screened but do not meet the criteria to undergo digital ABI. Those who were screened, do meet the criteria to undergo the digital ABI but choose not to will be asked if their data can still be used for this research study (and will be asked to sign a separate consent document).

c) If the proposed study is a clinical trial where a drug, vaccine, device or other treatment is compared to a placebo group or comparison treatment group, what are the guidelines or endpoints by which early decisions regarding efficacy or lack of efficacy can be made? For example, it may be reasonable to stop enrollment on a study when efficacy has already been clearly demonstrated, to avoid unnecessary enrollments of additional subjects. Alternatively, it may be reasonable to stop enrollment when it is clear that efficacy will never be demonstrated, given the statistical power of the study as designed. Describe the guidelines that are in place to assist in making these determinations, if relevant to the proposed study.

N/A

d) Describe how data analysis will be performed (statistical tests, methods of evaluating data) and indicate the smallest group/unit for which separate reporting will occur. For studies involving a questionnaire, if data and reliability information are available, please describe or provide references. For full board, unfunded studies describe sample size determination and power analysis. If none, please justify.

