Statistical analysis will be performed using R version 3.3.2 or newer (R Core Team, Vienna, Austria). Binary variables will be created for each sign, symptom, or risk factor based on the corresponding questionnaire response. Standard summary statistics will be calculated for study variables of interest. For continuous variables, statistics included the number of observations (N), mean, standard deviation, and 95% confidence interval. Categorical variables will be summarized in frequency distributions. The results of ABI will be categorized based on the ABI index obtained as normal (>0.9), calcified arteries (>1.4), Mild to moderate disease (0.4-0.9), Severed disease- <0.4 and compared to symptoms (e.g. asymptomatic, claudication, critical limb ischemia). A 'Positive ABI' will then be compared to gold standard 'angiography'; if angiography shows evidence of PAD, this will be termed 'angiographic positive'. Sensitivity will be defined as the proportion of 'ABI positive results' out of the number of samples which were actually 'angiographically positive'. When there are no positive results, sensitivity will not be defined and a value of NA is returned. Similarly, when there are no negative results, specificity will not be defined and a value of NA is returned. Similar statements will be true for predictive values. The positive predictive value will be defined as the percent of predicted positives that are actually positive while the negative predictive value will be defined as the percent of negative positives that are actually negative.

Please save frequently

Protocol Title:

Sensitivity and specificity of digital ankle brachial index (ABI) as a screening tool in detecting peripheral arterial disease: A single center, prospective clinical trial

e) State if deception (including incomplete disclosure of study purpose/procedures) will be used. If so, describe the nature of the deception and provide a rationale for its use. Also, describe debriefing procedures or justify a waiver of the requirement to debrief. NOTE: for studies using deception, an alteration of consent must be justified in the Informed Consent section of the protocol (#13) and the debriefing script/statement must be uploaded in the Attachments section (#16). See IRB Deception Guidelines.

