Protocol Title: Sensitivity and specificity of digital ankle brachial index (ABI) as a screening tool in detecting peripheral arterial disease: A single center, prospective clinical trial

Patients will be in the study until their results are obtained. If they qualify for further testing, they will receive standard of care treatment, but their records will be reviewed and information from their records will still be obtained.

The digital ABI test can be complete and results available in around 5 minutes.

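### Sensitivity and specificity are the primary aim, but no reference test is planned for participants with no evidence of PAD and no rule covers unverified participants

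*Combined protocol and SAP*

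**What the plan says.** - **Section 2b, primary aim:** "To evaluate the sensitivity and specificity of digital ABI in diagnosing PAD using color Doppler ultrasound and 'gold standard' angiography as reference".
- **Section 3b, step 7 (clinical course):** participants are divided on two items together, "If based on Screening questionnaire and digital ABI". Those diagnosed with PAD are telephoned and advised on further testing or referral. For the others: "There is no evidence of PAD- no further action will be taken".
- **Section 3d (data analysis):** "A 'Positive ABI' will then be compared to gold standard 'angiography". The formula is: "Sensitivity will be defined as the proportion of 'ABI positive results' out of the number of samples which were actually 'angiographically positive". No specificity formula is written. The nearest rule is that "when there are no negative results, specificity will not be defined and a value of NA is returned".
- **Section 8k (duration):** "Patients will be in the study until their results are obtained". Later record review is described for one group: "If they qualify for further testing, they will receive standard of care treatment, but their records will be reviewed".
- **Possible sources of reference results in negatives:** section 3b step 8 and expedited category 5 allow record access that is not limited to positives. Section 3f says that patients with signs and symptoms of PAD have traditional ABI or Doppler ultrasound at this hospital, and that some have angiography.
- **Continuing review, items 16, 20 and 21:** 238 usable participants, 44 positive (10 severe, 34 mild or moderate), of whom 8 severe and 2 mild or moderate were confirmed. Nothing is reported on disease status in the others. Enrolment is to rise from 400 to 750 to increase power.

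**The concern.** Sensitivity is a proportion of the diseased, and specificity a proportion of the disease-free. Both need disease status in people the device calls negative as well as in those it calls positive. The visible text creates a route to a reference result only for participants judged to have PAD, and does not say how anyone without a reference result enters the analysis.

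The study could therefore report a sensitivity that says nothing about the device, and a specificity that depends on a choice made at analysis. For a screening tool this matters most on the sensitivity side, because the cases the device misses are the ones nobody looks for.

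**Working it through.** **1. The plan's own figures.** The documents state no sensitivity, specificity or sample-size calculation. The only accuracy figures are the item 16 PPVs, and these do not follow from the counts beside them: 8/10 = 80% against a stated 67%, and 2/34 = 5.9% against a stated 14%. The stated values fit denominators of 12 (more than the 10 severe positives) and 14. This mismatch is a separate point. It is used here only because 2/14 = 14.3% raises the possibility that not all positives were verified.

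**2. The logic, which needs no counts.** Write TP, FP, FN and TN for the verified cells. If only positives are verified, FN = 0 and TN = 0 are observed.
- Sensitivity = TP/(TP + 0) = 100% for any device with at least one confirmed positive.
- Specificity among the verified = 0/(0 + FP) = 0% once one false positive is verified. If unverified negatives are counted as disease-free, it is instead high. The NA rule could also be read to return NA. The plan does not choose.

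**3. Size, for illustration.** Inputs from item 16: 238 usable, 44 positive, 10 confirmed. Hence 238 − 44 = 194 not called positive, and 44 − 10 = 34 unconfirmed positives. The PAD rate r among the 194 is not in the documents; 1%, 5% and 10% are assumed. FN = 194r, that is 1.94, 9.7 and 19.4.

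*Case A: all 34 unconfirmed positives are disease-free.* TP = 10, FP = 34.

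*Case B: 20 of the 34 are diseased.* This assumes that 14 mild or moderate positives were assessed. Then 14 − 2 = 12 were not confirmed; adding the 2 unconfirmed severe positives gives FP = 14. The other 34 − 14 = 20 are counted as diseased, so TP = 30.

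| r | Case A sensitivity, 10/(10 + FN) | Case B sensitivity, 30/(30 + FN) |
|---|---|---|
| 1% | 10/11.94 = 83.8% | 30/31.94 = 93.9% |
| 5% | 10/19.7 = 50.8% | 30/39.7 = 75.6% |
| 10% | 10/29.4 = 34.0% | 30/49.4 = 60.7% |

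With positives-only verification the planned formula reports 100% in all six cells.

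Counting all 194 as disease-free, specificity is 194/(194 + 34) = 85.1% in case A and 194/(194 + 14) = 93.3% in case B.

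**4. A few negatives verified through usual care.** Take case A at r = 5% and let a share v of the 9.7 missed cases be imaged (v is assumed). Verified-only sensitivity is 10/(10 + 9.7v): 95.4% at v = 5% and 67.3% at v = 50%, against 50.8% with full verification.

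**5. Enrolment.** Interim positivity is 44/238 = 18.5%. That gives about 74 positives at 400 and 139 at 750, and 750 × 194/238 = about 611 not called positive. If all are evaluable, all positives are verified and PPV is 10/44, the Wilson 95% half-width for PPV falls from about 9.4 points (17/74) to 6.9 points (32/139). The precision gained is for PPV; the 611 still have no planned reference test.

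**The case against.** The best defence is that positives-only verification is one reading of the text. Step 7 triages on questionnaire and ABI together, so a symptomatic ABI-negative participant might be sent for further testing. Record access is not limited to positives, and usual care images some symptomatic patients. The study calls itself a pilot, and its interim report discusses only PPV; no document reports 100% sensitivity. The data collection sheet and the consent documents are not visible.

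Part of this stands. A reader might infer that the plan rules out any reference result in a negative, or that the study will publish 100% and 0%. The documents do not support either: some verified negatives may arise, and the 100% is what the formula returns under positives-only verification, not a reported result. But access to charts is not a reference test. It retrieves only what usual care happened to order, selected by symptoms, while participants can enter on age, smoking or diabetes alone. Traditional ABI is also not a reference named in section 2b. Being a pilot does not alter the stated primary aim.

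The objection to taking the figures at face value also stands. A reader might take 85.1% as an upper bound on specificity. It is the highest value only with respect to missed cases among the 194. With respect to the 34 unconfirmed positives it is the lowest, since specificity rises if any of them are diseased (93.3% in case B). Nor is 50.8% an estimate of the device's sensitivity. The 10 were confirmed on follow-up examination and imaging, not necessarily angiography. The 194 may include results above 1.4, which section 3d labels as calcified arteries without assigning them to positive or negative.

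**Conclusion.** The concern holds for the text available. The plan does not provide what its primary aim needs: no reference test is planned for participants with no evidence of PAD, and no rule says how unverified participants are analysed. With positives-only verification the sensitivity formula returns 100% whatever the device's accuracy, and specificity is set by an unwritten choice. More enrolment does not remove this. Confidence is high on that structural claim, which rests on no counts.

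The size is illustrative only. Over assumed PAD rates of 1% to 10% in the 194, sensitivity runs from 83.8% to 34.0% in case A and from 93.9% to 60.7% in case B. These ranges depend on an unknown rate in the negatives and an unknown status of the unconfirmed positives. If usual care verifies some negatives, the remaining bias depends on who is imaged and cannot be computed from the documents. This should be resolved before enrolment proceeds toward 750.

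**What to change.** **First, under either option.** State one definition of the reference result in sections 2b and 3d, reconciling Doppler ultrasound and angiography (2b), angiography alone (3d) and follow-up examination and imaging (item 16). Say how an ABI above 1.4 is classified. Say in step 7 whether an ABI-negative participant can be placed in the PAD group.

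**Then choose one.**

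1. *Restate the primary endpoint* as the positivity rate and the PPV among positives with a reference result. Report the number verified by severity category, with PPV bounds that count unverified positives as all diseased and as none diseased. State that sensitivity, specificity and NPV are not estimable from positives-only verification. Disclose that the endpoint was changed after interim PPVs were known.
2. *Keep sensitivity and specificity.* Extend the section 8k record review to every ABI-negative participant over a fixed window, once consent and HIPAA cover is confirmed. Write the specificity formula and the rule for unverified participants. Report as the main result bounds over stated ranges of PAD prevalence in unverified negatives and in unverified positives. Use a verification-bias correction only if enough negatives have reference results, and state its missing-at-random assumption.

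**Cost.** Option 1 is wording plus a count of verified positives; the price is a narrower headline claim. Option 2 adds chart abstraction and one analysis, may need a consent or HIPAA change because participation ends once results are obtained, and will give wide bounds, since symptom-selected chart data cannot by themselves identify sensitivity. Neither adds a test for participants.
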